Participants will be ineligible for this study if they have:

- (1) baseline peripheral neuropathy greater than grade 1 (prior to receiving any doses of vincristine),
- (2) evidence of significant liver dysfunction,
- (3) Down's Syndrome,
- (4) pregnancy,
- (5) severe illness or infection,
- (6) current active treatment with erythropoietin,
- (7) administration of vitamin supplements above 100% of the recommended daily allowance

G. PATIENT RECRUITMENT

Potential subjects will be recruited from the Riley Hospital for Children (Riley) and IU North Hospital. Riley medicine doctors are dedicated to the care of pediatric, adolescent and young adults ages 1-25. Study personnel will work with the clinicians in the Riley Department of Hematology Oncology to obtain the names of patients who have diagnoses of acute lymphoblastic leukemia (ALL) or Non- Hodgkin's Lymphoma-lymphoblastic lymphoma (LL) and are planning to undergo vincristine treatment. Patients will be recruited during their first 4 weeks of vincristine treatment.

Potential minor subjects and their parents/legal guardians may be approached by their physician and/or study personnel with information about this study. Patients and their parents/legal guardians who are interested in participating in the study will undergo the informed consent process. Informed consent will be only obtained by trained and authorized study personnel or investigators. Patients and their parents/legal guardians may be given a study flyer with contact information at the time of consent.

After consent, eligibility will be verified by a member of the study team and the patient will be registered (i.e., enrolled) to this study. The original, signed, IRB-approved Informed Consent Document and all regulatory files will be maintained by the Pediatric Clinical Trials Office (PCTO). Applicable regulatory documents must be completed and on file prior to registration of any subjects.

H. RESEARCH DESIGN

This is a multi-center study to test the feasibility of pediatric and AYA patient adherence to a single intervention (exercise: EX) during the consolidation phase of vincristine treatment for Acute Lymphoblastic Leukemia or

Lymphoblastic Leukemia. Fitbit activity tracker data and questionnaires will be used for assessing adherence and feasibility. We will use a pre and post intent-to-treat design. Forty subjects will be recruited and enrollment is expected to last 24 months.

H.1 Sample size justification

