The Fitbit activity tracker was chosen for this feasibility study due to its versatility and effectiveness within younger populations of children. The FitBit's ease of use, comfort, design and feedback features were important factors for all age groups (children and AYA). Researchers in some studies utilized the Fitbit activity tracker to assess adherence to home-based activity programs⁷⁵.

I. PROCEDURES

[figure not shown]
I.1 Overview

For this feasibility study, 40 pediatric patients with a diagnosis of ALL or LL who have a TNS of ≥ 3 at the end of four weeks of vincristine treatment will be enrolled from Riley Hospital for Children, Indiana University Health North Hospital, . Children and AYA will be recruited during their first four weeks after diagnosis and if they have a TNS ≥ 3 at the time of baseline (week 4-6 T1) they will be enrolled into the study. During T1 patients will complete all questionnaires, neuropathy exams, and provide blood samples and then again at week 14 (T2). Neuropathy exam may be performed during weeks 4 through 6 to accommodate regimented clinical visits. Exercise assessments will be performed on week 7. Subjects will check-in with the exercise therapist during weeks 9, 11, and 13 at a minimum, or once a week during the study if they choose (weeks 7-15). These in-

person sessions will take approximately 15 minutes, and the therapist will provide education, evaluate the subject's exercise plan, review exercises, set goals, and make plans to optimize adherence to the exercise program.

All study visits will take place before or after routine clinic visits so that patients and their families do not have to make additional trips to the four hospital sites. EX sessions will be completed by patients at home using instructional videos that will be given to participants during their study orientation.

I.2 Intervention timeline

I.3 Exercise (EX) Intervention

The EX intervention will include both an in-person exercise schedule and at-home video EX sessions (See Appendix I and II). The EX intervention will be designed and led by an AFAA (Athletics and Fitness Association of America) certified physical fitness trainer with fifteen years' experience and a professional with a PhD in an Exercise Science related field.

In-Person Exercise Sessions:

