The first session will be completed at one of the four hospital sites with the EX intervention specialist during the baseline visit. Patients will check-in with their intervention specialist during routine visits to one of the sites or phone on weeks 8, 10, and 12 at a minimum throughout consolidation treatment, or once per week if they choose (weeks 7-15). In-person sessions will last approximately 15 minutes each during which time the therapist will provide *education* on the importance of exercise for VIPN, review the exercises, reassess difficulty level, *set exercise goals* for the following week, and *plan* to reach these goals. Reviewing exercises will demonstrate that the patient has learned exercises through *observational learning* from the therapist and peer models on the exercise videos. In-person sessions will also allow the therapist to provide *reinforcement* for the patient's progress.

If the patient or the study team are unable to meet in person the intervention specialist will contact the patient via their prefer contact method (phone call, email, Skype). These sessions will follow the format of the in-person sessions. Education, assessment of difficulty level, set exercise goals and plan will all be discussed during the remote check-in.

Home Exercise Sessions:

At baseline, participants will have access to the exercise videos via the study website or they will be downloaded to the study tablet, with 3 chapters of EX sessions to be completed at home with video instruction. Patients will be asked to complete home EX sessions 6 times per week for 8 weeks (week 6 through week 13) during the consolidation phase of treatment. A Daily Exercise Log is available to record exercise chapters, fatigue level and time of day exercised (See Appendix III). Patients may choose their rest day each week. Each EX session will last approximately 15 minutes. The at-home videos will have the therapist and three children and AYA who are of similar age to the patients demonstrate the exercises. This design is critical for supporting the *observational learning* component of the intervention. Two videos will be available for the study: one for ages 5 – 10; one for ages 11 – 25.

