To address Aim 1, adherence in the intervention group will be measured through a 5 question survey at each treatment and also through start/stop on the Fitbit. Adherence scores will be summarized across time with descriptive statistics (N, mean, SD, median, minimum, and maximum). From start/stop information, the proportion of exercise sessions completed and the proportion of patients which complete at least 50% of the exercise sessions along with associated 95% confidence intervals will be estimated. Additionally, descriptive statistics will be provided for the patient satisfaction survey provided at the end of the study.

To address Aim 2, we will use paired t-tests to examine change from baseline (T1) to 14 weeks (T2). For outcomes which are known to be non-normal such as biomarkers, we will use Wilcoxon-signed rank tests. We plan an intent-to-treat analysis. Even if we do not see significant differences, descriptive statistics including means, SD, and effect sizes (differences in means between the two time points divided by pooled SD) will be reported for outcomes along with 95% confidence intervals. All analysis will include checking of assumptions. Additionally, we will also use repeated measures ANOVA to estimate the contrast of interest (change from baseline at 14 weeks) for primary and secondary outcomes, after adjusting for age and baseline activity level.

For activity outcomes obtained from the FitBit, such as patients' daily number of steps, distance, active minutes, and heart rate, we will start with simple techniques such as paired t-tests or Wilcoxon signed-rank tests to compare the mean change in activity level from baseline (T1: summarized over week 6) to treatment end (T2: summarized over week 13). As an exploratory analysis, we will also use a generalized linear mixed model with appropriate distribution (e.g. Poisson) and link function fit to all weekly outcomes to examine changes over time using time as a continuous variable. We expect to have an abundance of information provided from the Fitbit, thus we will estimate descriptive statistics (N, mean, SD, median, minimum, and maximum) for all outcomes (i.e., number of steps, distance, active minutes, and heart rate) at each week to aid in planning future studies.

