Based on our conceptual model, we will also examine associations between change scores for predictors and change scores for primary and secondary outcomes. For example, we will estimate Pearson correlations between changes in self-efficacy, outcome expectations, support, neuropathy, pain, and quality of life.

We will also examine whether or not the circulating protein biomarkers at T1 are associated with VIPN severity at T1 using Spearman correlations and whether initial or dynamic levels of the circulating biomarkers are predictive of intervention efficacy. The associations between VIPN and the genetic and circulating biomarkers will be analyzed through generalized linear mixed models, which includes a random subject effect to account for the correlation of observations from the same subject.

J.3 Missing Data

We expect minimal dropout at 14 weeks (primary endpoint for the proposed trial) and have inflated the sample size to account for the expected 15% attrition, so we anticipate it will not create any substantial bias in the results. To aid in future studies, we will compare baseline characteristics among those who complete the study and those who do not to determine if there are any characteristics associated with study completion.

K. RISKS OF PARTICIPATION AND PROTECTION OF HUMAN SUBJECTS

K.1 Risks

Possible risks to participation in this study are breach of confidentiality, physical distress or emotional distress due to study participation. All contact with the participant will be documented beginning at the consent process through completion of the study. All documentation will be reviewed regularly. Any events that might indicate increased participant physical distress or emotional distress will be promptly brought to the attention of the PI and reported to the IRB and DSMC per reporting guidelines listed below. We will promptly report to the IRB any instances of consent withdrawal due to distress. The IRB will be informed at least annually of our data and safety monitoring, summary of participant status, and any changes in the risk of the study.

Prevention of injuries have been addressed through 1) video design, 2) safety reminders during videos and fitness assessment and 3) muscle soreness. The video design is based on a specific gradual workout design to ensure safety for the most deconditioned patients. The study has incorporated beginner (seated or bed), intermediate (bridge between beginner and advanced) and advanced EX chapters.

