
Criteria for removal from the study are as follows:

- The participant expresses significant distress related to completion of the study (the PI will refer the participant to clinical services if needed).
- The participant provides verbal or written notification that s/he has decided to discontinue study participation.

Any other reason for which the principal investigator believes the participant should be withdrawn.

M. PATIENT CONSENT AND PEER JUDGEMENT

The protocol and informed consent form for this study must be approved in writing by the appropriate Institutional Review Board (IRB) prior to any patient being registered on this study.

Changes to the protocol, as well as a change of principal investigator, must also be approved by the Board. Records of the Institutional Review Board review and approval of all documents pertaining to this study must be kept on file by the investigator and are subject to inspection at any time during the study. Periodic status reports must be submitted to the Institutional Review Board at least yearly, as well as notification of completion of the study and a final report within 3 months of study completion or termination.

The study will be conducted in compliance with ICH guidelines and with all applicable federal (including 21 CFR parts 56 & 50), state or local laws.

N. REFERENCES

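### Section L provides only for removal from the whole study, with no T2 assessment afterwards, so removed patients drop out of the Aim 2 paired analysis despite the intent-to-treat label

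*Combined protocol and SAP*

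**What the plan says.** Section L opens with "Criteria for removal from the study are as follows" and lists three routes. The first is distress: "The participant expresses significant distress related to completion of the study". The second is the participant's own notice of leaving. The third is discretionary: "Any other reason for which the principal investigator believes the participant should be withdrawn". All three lead to the same outcome, removal from the study. The section does not describe leaving the exercise programme while staying in data collection, and no other section provides for a T2 assessment after removal.

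Section H states "We will use a pre and post intent-to-treat design", and Section J.2 repeats "We plan an intent-to-treat analysis". The main Aim 2 method in J.2 is a paired t-test of T1 against week 14. J.2 adds a repeated measures ANOVA adjusted for age and baseline activity, without saying how incomplete pairs enter it.

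Section J.3 relies on the 15% inflation of the sample size and a baseline comparison of completers with non-completers. It expects no substantial bias.

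Section K.1 treats distress as foreseeable: "Possible risks to participation in this study are breach of confidentiality, physical distress or emotional distress due to study participation". On logistics, Section I.1 says "All study visits will take place before or after routine clinic visits".

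**The concern.** An intent-to-treat reading of a pre–post study needs the T2 outcome from everyone enrolled, however they fared with the intervention. A paired test uses only patients with both values. A patient removed under the distress or investigator criterion therefore leaves the analysis, even if willing to be examined at week 14.

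If the reasons for removal are linked to how neuropathy develops, the patients who remain are a selected group. Their mean change then differs from that of all enrolled patients. Section B places the peak of intermediate to severe neuropathy around week 14, which is T2, and Section I.3 sets a demanding schedule: "Patients will be asked to complete home EX sessions 6 times per week for 8 weeks". A link between worsening neuropathy and distress is therefore plausible, though not established. Enrolling extra patients protects precision but does not remove this kind of bias. Aim 2 exists to supply effect sizes for planning a later efficacy trial, so a biased change would carry forward.

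**Working it through.** **1. The plan's own figures (Section H.1).** Inputs: 40 enrolled, 15% attrition, SD 3.66 at both times, correlation 0.4, a 2-point TNS-PV change, type I error 0.05. H.1 states a two-sided test for the other outcomes; I assume the same for TNS-PV.

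- Completers: 40 × 0.85 = 34, so 6 losses are budgeted.
- SD of change: 3.66 × √(2 × (1 − 0.4)) = 4.009.
- Standardised change: 2 / 4.009 = 0.499.
- Paired t-test power (noncentral t, n − 1 degrees of freedom): 0.806 at n = 34.

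The stated 80% reproduces. There is no arithmetic error and no power shortfall at the planned 34.

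**2. What further T2 values could add to power.** At n = 40 the same calculation gives 0.868. That is a ceiling, because some patients will decline or withdraw consent.

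**3. Bias from outcome-related removal.** Let k of 40 be removed, with a mean change g points worse than that of the patients who stay, whose mean change is m. The all-enrolled mean is ((40 − k)m + k(m + g))/40 = m + kg/40. The stayers' mean is therefore too favourable by (k/40) × g.

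The documents give neither k nor g, so both are assumed. I take k from 1 up to the full attrition allowance of 6, and g from 1 to 4 points.

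| Removed (k) | g = 1 | g = 2 | g = 4 |
|---|---|---|---|
| 1 | 0.025 | 0.05 | 0.10 |
| 2 | 0.05 | 0.10 | 0.20 |
| 4 | 0.10 | 0.20 | 0.40 |
| 6 | 0.15 | 0.30 | 0.60 |

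Against the 2-point meaningful change, the range is 0.025/2 = about 1% to 0.60/2 = 30%.

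**4. Effect on the test.** Suppose the true change in all 40 were zero and the SD of change in the stayers were 4.009. The chance of a significant apparent improvement, nominally 2.5% in that direction, becomes:

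- k = 2, g = 2: 3.5%
- k = 6, g = 1: 4.0%
- k = 6, g = 2: 6.2%
- k = 6, g = 4: 13.3%

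The last row is the extreme corner of the assumed range.

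**The case against.** The strongest reply is that Section L removes fewer patients than it might seem to, and that the plan is silent on T2 after removal rather than against it. Much of this stands, and it rules out several stronger readings.

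- **That patients who stop exercising lose their T2 assessment.** Section L has no such criterion. A patient who stops without study-related distress, withdrawal or an investigator decision stays in. Section I.1 schedules T2 without an adherence condition, and adherence is itself an Aim 1 outcome.
- **That the distress criterion singles out patients least suited to exercise.** The wording concerns distress about completing the study, which could equally come from questionnaires, examinations or blood draws.
- **That the plan forbids a T2 exam after removal.** It does not. The loss follows from removal combined with the absence of any follow-up provision. The consent text is not in the documents reviewed and may address this.
- **That the missing values are beyond any analysis.** Sensitivity analyses can bound their effect, and methods using the observed data can address it under assumptions that cannot be tested. The plan names neither.
- **That all six budgeted losses come from this rule.** Section H.1 gives 15% as overall attrition, with no breakdown by cause.

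Two further points also stand. Distress need not track TNS-PV change, so the direction of bias is assumed. Section K.1 foresees withdrawal of consent because of distress, and follow-up cannot be sought from those patients.

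The reply does not remove the remaining gap. For a patient removed for distress or at the investigator's discretion who would agree to be examined, the plan as written obtains no T2 value, and neither J.2 nor J.3 says what the intent-to-treat analysis then does.

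**Conclusion.** The point holds in a limited form. Section L's single outcome, with no provision for T2 afterwards, sits poorly with the intent-to-treat design and analysis stated in H and J.2, and J.3 does not fill the gap. The issue is bias and the meaning of the label, not power.

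The illustrated bias of 0.025 to 0.60 TNS-PV points rests entirely on assumed values for the number removed and the gap in their outcomes. With one or two removals it is at most 0.20 points; the upper end needs all six budgeted losses to be removals of this kind with a 4-point gap. This is a cheap improvement worth making in a small feasibility study, not a flaw that invalidates it.

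**What to change.** Reconcile Section L with H, J.2 and J.3:

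- In L, distinguish ending the exercise programme from withdrawing from data collection.
- Where a participant is taken off the programme for distress or by investigator decision and has not withdrawn consent, ask whether they are willing to have the T2 neuropathy exam at the week-14 routine visit, with questionnaires and blood if they agree.
- In J.2 and J.3, state that these participants stay in the Aim 2 analysis, and say how patients who still lack T2 are handled.

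No clinical criterion for stopping exercise or for removal is proposed; those decisions stay with the study team.

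The cost is a short amendment to L, matching lines in J.2 and J.3, and a change to the consent text if it says otherwise. Study visits already take place around routine clinic visits, so no extra trip should be needed. The downside is a small burden on patients who have left the programme, some of whom will decline.
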